6.12.2 Laboratory Data

Laboratory data will be collected at Screening, Weeks 2, 7, 13, 18, 26 and 42.

Hematology tests will include CBC with differential, platelet count and coagulation (prothrombin time (PT) and partial prothrombin Time (PTT)) studies.

Clinical chemistry tests will include sodium, potassium, chloride, bicarbonate, blood urea nitrogen (BUN), creatinine, estimated creatinine CL, glucose, calcium, CO₂, total protein, albumin, ALP,

QMD Ref: Worldwide-TMP-ST-005-7.0 Effective: 12Aug2019	Governing QMD: Worldwide-SOP-ST-001
Confidentiality Statement	
This document is the property of Worldwide Clinical Trials Inc. and may not be duplicated, copied, altered or removed from company without prior approval from Worldwide Quality Assurance or in compliance with Worldwide Standard Operating Procedures.	

Worldwide Clinical Trials Controlled Quality Management Document		
 WORLDWIDE CLINICAL TRIALS	Sponsor:	Synaptogenix, Inc.
	Protocol Number:	NTRP-101-204
STATISTICAL ANALYSIS PLAN. PHASE 2-3-4		

ALT, AST, gamma glutamyl transferase (GGT) lactate dehydrogenase (LDH), uric acid and bilirubin.

A serum creatine phosphokinase (CPK) will be done at screening and in the event of myalgia. A Thyroid-Stimulating Hormone (TSH) analysis will be done at screening, and B12, T-3 and T-4 will be done if TSH result is abnormal.

Test for β hCG will be performed if indicated.

Test for HbA1C will be performed if clinically indicated.

Descriptive statistics of the observed values and change from baseline (continuous data) will be presented by treatment group and visit **only for hematology tests and clinical chemistry tests**. Each measurement (continuous data) will be classed as below, within, or above normal range, based on ranges supplied by the laboratory used. Shift tables in relation to the normal range from baseline to each follow-up visit will be presented.

Data on CPK, TSH (and corresponding tests), β hCG and HbA1C will not be tabulated.

All laboratory data will be presented in listings.

6.12.3 Vital Signs

Vital signs will be collected at Screening and each study visit. At dosing visits, collection will be performed prior to infusion and at 30, 60 and 90 minutes from start of the infusion (+/- 5 minutes) Descriptive statistics for observed values and changes from baseline in the following vital signs will be presented by treatment group and visit:

- Systolic blood pressure (mmHg)
- Diastolic blood pressure (mmHg)
- Pulse rate (bpm)
- Respiration rate (breath / min)
- Body temperature

For the calculation of descriptive statistics the values of body temperature measured in Fahrenheit will be transformed using the following formula: $[\text{value in } ^\circ\text{C}] = ([\text{value in } ^\circ\text{F}] - 32) \times 5/9$.

All data on vital signs will be listed.

QMD Ref: Worldwide-TMP-ST-005-7.0 Effective: 12Aug2019	Governing QMD: Worldwide-SOP-ST-001
Confidentiality Statement	
This document is the property of Worldwide Clinical Trials Inc. and may not be duplicated, copied, altered or removed from company without prior approval from Worldwide Quality Assurance or in compliance with Worldwide Standard Operating Procedures.	

Worldwide Clinical Trials Controlled Quality Management Document		
 WORLDWIDE CLINICAL TRIALS	Sponsor:	Synaptogenix, Inc.
	Protocol Number:	NTRP-101-204
STATISTICAL ANALYSIS PLAN. PHASE 2-3-4		

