2 CLINICAL TRIAL DATA

2.0 Oncology Data

Safety data are available from published clinical studies of bryostatin for the treatment of cancer. Altogether, over 1400 oncology subjects received bryostatin, mainly under NCI's IND # 42,780, with exposures to bryostatin in both single and combination agent studies. About 584 subjects received bryostatin as monotherapy, with dose levels ranging from 5 μ g/m² to >180 μ g/m². Most subjects in both the monotherapy and combination therapy studies received bryostatin at doses >25 μ g/m², most often as 1-hour infusions administered at various time intervals from weekly infusion to continuous infusions for 72 hours. Most studies were repeated dose studies where subjects received treatment for several weeks (See Investigators Brochure).

Adverse events occurring in the single agent studies that resulted in discontinuation from the studies were myalgia (28 subjects), acute transient reaction (dyspnea, flushing, hypotension, and bradycardia; 4 subjects each), phlebitis (attributed to ethanol in the formulations, 6 subjects), fatigue (3 subjects), and 1 subject each with bacteremia, chest pain, dehydration,

CONFIDENTIAL

dysphagia, hematuria, nausea, skin rash, subclavian vein thrombosis, thrombocytopenia, and vomiting. The following AEs were associated with death in the single agent trials: cardiac arrest (2), hypotensive with evidence of renal and hepatic failure (1), perforated gastric ulcer (1), renal function decline with cardiac arrest and perforated gastric ulcer (1; PIs considered not related to bryostatin), and sudden death (1; PIs considered likely to be cardiovascular event). Relatedness to bryostatin treatment was not assessed except where noted.

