4.1 Dose Rationale

The primary objective of treatment for cognitive disorders with bryostatin is activation of PKC ϵ , not downregulation as was attempted for the oncology indications. Bryostatin activation of PKC ϵ is dose dependent, where lower doses activate PKC ϵ and increase de-novo synthesis of the enzyme, while higher doses of bryostatin downregulate PKC ϵ .

The dosing regimen is based on the recently completed phase 2 study, NTRP101-202, in which the safety and efficacy analyses indicated a clear advantage of the 20 μ g dose over the 40 μ g dose.

The oncology data suggest that the dose-limiting side effect of myalgia is dose dependent and cumulative and likely related to the down regulation of PKC ϵ . This was not seen in the NTRP101-201 study, in which there were no reports of myalgia after a single 25 μ g/m² dose of bryostatin was administered, nor in the recently completed NTRP101-202 study, in which myalgia was considered an adverse event of special interest. In NTRP101-202, in which subjects received 7 doses of study drug, myalgia was seen in 5 subjects; 4 of those subjects were given the higher 40 μ g dose of bryostatin. Myalgia observed was mostly mild and managed with analgesics.

Dosing in this study will begin with two initial loading doses at one-week intervals that are 20% higher than the maintenance dose (i.e., 24 μ g) to assure enzyme activation. Dosing will then continue with 20 μ g administered every other week for 5 weeks, for a total of 7 doses. The first treatment period will occur over 15 weeks, including a follow-up visit 30 days after the last dose. The same treatment regimen will be administered for subjects who qualify for a second course of treatment. The total study drug administered to a particular subject is 14 doses.

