6.1.17 Week 26 (Day 182 \pm 2 days Dose 14)

- Prior to dosing:
 - C-SSRS
 - Blood samples for routine safety
 - 12-lead ECG
 - Abbreviated Physical exam
- Vital signs prior to infusion, then at 30(\pm 5), 60(\pm 5) and 90(\pm 5) minutes from start of the infusion
- *Dosing by IV infusion*
- Adverse events and concomitant medications

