9.8.4 Vital Signs

Tabulations of raw data and change from baseline values will be presented by time point for each vital sign parameter.

Tabulations will include the number of observations, mean, standard deviation, median, and minimum and maximum values. For change from baseline summaries, subjects with an undefined change from baseline, because of missing data, will be excluded.

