6.2.2 Baseline

Baseline is defined as the last non-missing value (either scheduled, unscheduled or repeat) before the subject receives the first dose of study drug.

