14.3.1.4	Patients with Treatment Emergent Adverse Events by Maximal Relationship to Study Treatment	IP	
14.3.1.5	Serious Treatment Emergent Adverse Events	IP	
14.3.1.6	Treatment Emergent Adverse Events Resulting in Discontinuation of Study Treatment	IP	
14.3.1.7	Patients with Treatment Emergent Adverse Events Resulting in Discontinuation of Study Treatment by Maximal Relationship to Study Treatment	IP	
14.3.1.8	Patients with Treatment Emergent Adverse Events that Lead to Study Discontinuation by Maximal Relationship to Study Treatment	IP	
14.3.1.9	Patients with Serious Treatment Emergent Adverse Events by Maximal Relationship to Study Treatment	IP	
14.3.1.10	Treatment Emergent Adverse Events of Special Interest	IP	
14.3.4	Abnormal Laboratory Values		
14.3.4.1	Hematology, Measured Values and Changes from Baseline by Visit	IP	
14.3.4.2	Hematology, Shifts from Baseline to Post-Baseline Visits	IP	
14.3.4.3	Clinical chemistry, Measured Values and Changes from Baseline by Visit	IP	

QMD Ref: Worldwide-TMP-ST-005-7.0 Effective: 12Aug2019

Governing QMD: Worldwide-SOP-ST-001

Confidentiality Statement

This document is the property of Worldwide Clinical Trials Inc. and may not be duplicated, copied, altered or removed from company without prior approval from Worldwide Quality Assurance or in compliance with Worldwide Standard Operating Procedures.

Worldwide Clinical Trials Controlled Quality Management Document

**WORLDWIDE
CLINICAL TRIALS**

Sponsor:

Synaptogenix, Inc.

Protocol Number:

NTRP-101-204

STATISTICAL ANALYSIS PLAN. PHASE 2-3-4

Table Number	Table Title	Validation Method	Shell Number (if repeat)
14.3.4.4	Clinical chemistry, Shifts from Baseline to Post-Baseline Visits	IP	
14.3.5	Extent of Exposure, Dosage Information and Compliance		
14.3.5.1	Exposure	IP	
14.3.6	Vital Signs and Physical Examination		
14.3.6.1	Vital Signs, Measured Values and Changes from Baseline by Visit	IP	
14.3.6.2	Weight and BMI, Measured Values and Changes from Baseline by Visit	IP	
14.3.6.3	Physical Examination	IP	
14.3.7	Other Safety		
14.3.7.1	Electrocardiogram, Measured Values and Changes from Baseline by Visit	IP	
14.3.7.2	Electrocardiogram, Shift in Overall interpretation from Baseline to Post-Baseline Visits	IP	
14.3.7.3	Columbia-Suicide Severity Rating Scale (C-SSRS) at Screening	IP	
14.3.7.4	Columbia-Suicide Severity Rating Scale (C-SSRS) at Post-baseline Visits	IP	
14.3.8	Concomitant Medication		
14.3.8.1	Prior Medications. Safety Analysis Set	IP	

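### No within-visit change in vital signs is planned, so for 13 of 14 infusions the reported change mixes the acute effect with 1 to 26 weeks of between-visit variation

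*SAP*

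**What the plan says.** SAP 6.12.3 sets the collection at dosing visits: "collection will be performed prior to infusion and at 30, 60 and 90 minutes from start of the infusion". It then gives the summary: "Descriptive statistics for observed values and changes from baseline in the following vital signs will be presented by treatment group and visit". All vital-sign data are also listed.

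The reference value comes from SAP 6.2.2: "Baseline is defined as the last non-missing value (either scheduled, unscheduled or repeat) before the subject receives the first dose of study drug". This is the only baseline definition in the SAP and it applies to every variable.

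The SAP's list of outputs has one vital-signs table, 14.3.6.1, titled "Vital Signs, Measured Values and Changes from Baseline by Visit". Protocol 9.8.4 words the presentation differently: "Tabulations of raw data and change from baseline values will be presented by time point for each vital sign parameter". The SAP states in Section 6 that its methods take precedence over the protocol's.

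On the number of infusions, Protocol 4.1 says: "The total study drug administered to a particular subject is 14 doses". Protocol 6.1.17 puts the fourteenth at Week 26, Day 182.

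**The concern.** One reading before the infusion and three timed readings after its start make a design for detecting acute infusion effects. The natural reference for such an effect is the reading taken just before that infusion. The plan collects it, but after dose 1 does not use it as the reference.

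These readings have some weight in the safety assessment. In study NTRP101-202 the median time of peak concentration was the end of the 45-minute infusion (Protocol 2.1.2.5), so the 30- and 60-minute readings lie on either side of it. ECGs do not fill the gap: at Weeks 7, 18 and 26 they are done before dosing, and Weeks 2 and 13 are not dosing visits. Protocol 2.0 lists among the reasons for stopping in the single-agent oncology studies "acute transient reaction (dyspnea, flushing, hypotension, and bradycardia; 4 subjects each". Safety is part of the primary objective (Protocol 3.0).

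Laboratory and ECG results get shift tables (SAP 6.12.2 and 6.12.4). Vital signs get group descriptive statistics only, in which a sharp fall in a few subjects is easily lost.

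**Working it through.** **1. Count of infusions.** The visit schedule (Protocol 6.1.2 to 6.1.17) gives dosing days 0, 7, 21, 35, 49, 63, 77, 105, 112, 126, 140, 154, 168 and 182. That is 14, as Protocol 4.1 states.

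**2. Infusions whose reference is not the same-day reading.** For dose 1 the Day 0 pre-infusion value, if recorded, is also the study baseline. Every later dose is referred back to it:
- infusions: 14 - 1 = 13;
- timed readings: 13 x 3 = 39 of 14 x 3 = 42;
- nominal age of the reference in weeks: 1, 3, 5, 7, 9, 11, 15, 16, 18, 20, 22, 24, 26 (sum 177; mean 177/13 = 13.6; median 15).

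**3. What the planned change contains.** Let B be the study baseline, P the pre-infusion value at a visit and Y a timed reading at that visit. Then

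Y - B = (P - B) + (Y - P).

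The first term is between-visit variation and the second is the acute change. As an illustration with assumed values, an acute fall of 8 mmHg appears as -13 if the subject has drifted by -5 since baseline, and as -3 if the drift is +5.

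**4. Effect on spread.** With equal variances, SD(change) = SD x sqrt(2(1 - r)). The ratio of the within-visit SD to the planned SD is therefore sqrt((1 - r_same day)/(1 - r_across weeks)). The documents give no correlations, so both are assumed and varied:
- 0.9 and 0.4: sqrt(0.1/0.6) = 0.41;
- 0.8 and 0.5: sqrt(0.2/0.5) = 0.63;
- 0.7 and 0.5: sqrt(0.3/0.5) = 0.77;
- 0.7 and 0.6: sqrt(0.3/0.4) = 0.87.

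Over 0.7 to 0.9 and 0.4 to 0.6 the within-visit SD is 41% to 87% of the planned SD. Equivalently, the planned SD is 1.15 to 2.45 times the within-visit SD.

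**5. What observed values can recover.** If means are shown for each reading time, mean(Y) - mean(P) equals the mean within-visit change when the same subjects contribute to both. Its SD cannot be obtained this way, because it needs the correlation between P and Y, which is not tabulated. Individual falls cannot be obtained either.

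**6. SAP against protocol.** The protocol commits to presentation per time point. The SAP text and its table title commit only to presentation per visit. The SAP therefore does not say that the 30-, 60- and 90-minute values will appear separately, and the recovery in step 5 depends on that.

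**The case against.** The strongest reply is that the plan already contains most of what is needed. Observed values are summarised as well as changes, everything is listed, and the trial is randomised 1:1 against placebo, so seasonal or background drift common to both arms cancels in expectation in the between-arm comparison. Change from baseline is what the protocol asks for. No hypothesis test is planned on vital signs (Protocol 9.3). Symptomatic reactions are also captured as adverse events, and systemic hypersensitivity reactions go to the Medical Monitor immediately. The oncology signal came from uncontrolled studies, mostly at doses above 25 µg/m². In the Alzheimer's studies, NTRP101-201 saw no clinically significant vital-sign change after a single dose, and NTRP101-202 saw no apparent arm differences in most vital signs.

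Most of this stands, and it sets the size of the point. It leaves three gaps:
- Placebo does not remove the added noise, the effect of differential dropout, or drift caused by the drug. The last is conceivable: in NTRP101-202 mean weight changed by -1.65 kg on 20 µg and +0.442 kg on placebo.
- Subtracting observed means works only if they are shown per reading time, and it yields no SD and no individual falls.
- Pairing up to 42 timed readings per subject and parameter by hand from a listing is not a planned summary.

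A reader might infer more than the documents support. They do not show that the treatment comparison is biased by drift, for the reason just given. They do not show that the timed readings will be pooled or omitted; the SAP leaves this open. The 13 infusions do not all carry weeks of drift, since dose 2 falls on Day 7 (window ±2 days). Nor would acute reactions go unseen, since adverse-event recording is a separate route.

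**Conclusion.** The point holds as a gap in a descriptive safety summary. Neither document plans a within-visit change, and for 13 of 14 infusions (39 of 42 timed readings) the planned change is measured from a value nominally 1 to 26 weeks old although a same-day reference is collected. This follows from the text and the schedule and rests on no assumption.

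The loss of precision does rest on assumptions. The range of 41% to 87% depends on correlations that the documents do not give, and at its upper end the gain is modest. The documents also report no size for blood-pressure drift.

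No efficacy endpoint, formal test or sample-size figure is affected. Severity: minor.

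**What to change.** In SAP 6.12.3 and Table 14.3.6.1:
- Present the pre-infusion, 30-, 60- and 90-minute values separately, in line with Protocol 9.8.4.
- For every dosing visit, add the change at 30, 60 and 90 minutes from that visit's pre-infusion value, by arm, visit and time point.
- Summarise each subject's largest within-visit fall in systolic pressure and in pulse, visit by visit. Do not pool it over all visits: the largest of many falls depends on how many infusions a subject received, and that may differ between arms.
- Keep change from study baseline for the pre-infusion readings and the non-dosing visits, where longer-term change is the question.

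The cost is one derived variable and one more descriptive table. No new data are needed.

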6.12.4 Electrocardiogram Data

Electrocardiogram (ECG) will be performed at Screening (triplicate), Weeks 2, 7, 13, 18 and 26. Descriptive statistics for ECG interpretation results will be presented in a table. Interpretation results and changes from baseline will be presented in a shift table.

Electrocardiogram data will also be presented in a listing.

6.12.5 Physical Examination

Physical examination (PE) will be performed at Screening, Weeks 7 (abbreviated), 13, 18, 26 and 42. It will include, but is not limited to the following:

- General appearance
- Weight
- Height (screening only)
- Ears
- Eyes
- Nose
- Throat
- Neck
- Respiratory system
- Cardiovascular system
- Abdomen
- Musculoskeletal /Neurologic
- Extremities
- Skin
- Lymph nodes

An abbreviated PE will include but is not limited to the following:

- General appearance
- Weight
- Respiratory system
- Cardiovascular system

QMD Ref: Worldwide-TMP-ST-005-7.0 Effective: 12Aug2019	Governing QMD: Worldwide-SOP-ST-001
Confidentiality Statement	
This document is the property of Worldwide Clinical Trials Inc. and may not be duplicated, copied, altered or removed from company without prior approval from Worldwide Quality Assurance or in compliance with Worldwide Standard Operating Procedures.	

Worldwide Clinical Trials Controlled Quality Management Document		
 WORLDWIDE CLINICAL TRIALS	Sponsor:	Synaptogenix, Inc.
	Protocol Number:	NTRP-101-204
STATISTICAL ANALYSIS PLAN. PHASE 2-3-4		

- Abdomen

For the calculation of descriptive statistics, the values of weight measured in LB will be transformed using the following formula: [value in °KG] = [value in °LB] × 0.45359.

Values of weight and changes from baseline will be tabulated with descriptive statistics.

Assessment results and changes from baseline for each body system will be presented in shift tables.

Results of physical examinations will be listed.

6.12.6 Columbia Suicide Severity Rating Scale

Columbia Suicide Severity Rating Scale (C-SSRS) will be collected at screening, Weeks 2, 7, 13, 18, 26 and 42. Results will be presented in a table with descriptive statistics and in a listing.

7 INTERIM ANALYSIS

No interim analyses are planned.

8 DATA SAFETY MONITORING BOARD ANALYSIS

Safety data will be reviewed by Data Safety Monitoring Board (DSMB) when 30 subjects have received four doses of study drug, followed by additional safety analyses when 60 subjects have received a similar number of doses. Following tables and listings will be prepared for DSMB review:

Tables:

- Demographic data
- Disease history
- Medical history
- Summary of TEAEs
- Summary of TEAEs by relationship to clinical trial treatment
- Summary of Serious TEAEs
- Summary of Serious TEAEs by relationship to clinical trial treatment

QMD Ref: Worldwide-TMP-ST-005-7.0 Effective: 12Aug2019	Governing QMD: Worldwide-SOP-ST-001
Confidentiality Statement	
This document is the property of Worldwide Clinical Trials Inc. and may not be duplicated, copied, altered or removed from company without prior approval from Worldwide Quality Assurance or in compliance with Worldwide Standard Operating Procedures.	

Worldwide Clinical Trials Controlled Quality Management Document		
 WORLDWIDE CLINICAL TRIALS	Sponsor:	Synaptogenix, Inc.
	Protocol Number:	NTRP-101-204
STATISTICAL ANALYSIS PLAN. PHASE 2-3-4		

- Summary of Adverse Events of Special Interest (AESI)
- Summary of AESI by relationship to clinical trial treatment

Listings:

- Demographic data
- Disease history
- Medical history
- Pre-treatment AEs
- TEAEs
- Serious TEAEs
- TEAEs resulting in discontinuation of study treatment
- TEAE with fatal outcome

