A total of 97 (68.8%) subjects in all treatment groups reported 287 separate TEAEs. Of these, 49 (34.8%) subjects reported 107 separate treatment-related TEAEs. There were 8 (16.7%) subjects with 20 treatment-related TEAEs in the placebo treatment group, 17 (37.0%) subjects with 30 events in the 20µg bryostatin treatment group, and 24 (51.1%) subjects with 57 events in the 40µg bryostatin treatment group. Six subjects had a TEAE that lead to trial drug discontinuation, 2 in the placebo treatment group, 1 in the 20µg bryostatin treatment group, and 3 in the 40µg bryostatin treatment group. Overall, 43 (30.5%) subjects had a TEAE that was mild in intensity, 46 (32.6%) subjects had a TEAE that was moderate in intensity, and 8 (5.7%) subjects had a TEAE that was severe in intensity.

CONFIDENTIAL

There was 1 death in the trial, a subject in the 40µg bryostatin treatment group who suffered a severe TEAE of worsening of AD that was unrelated to the IP.

There were 12 (8.5%) subjects who had 14 treatment emergent non-fatal SAEs during the trial; 4 subjects with 4 events in the placebo treatment group, 2 subjects with 2 events in the 20µg bryostatin treatment group, and 6 subjects with 8 SAEs in the 40µg bryostatin treatment group. A total of 4 subjects in the 40µg bryostatin treatment group had 4 events that were judged as possibly or probably related to the IP: 3 events of cellulitis, and 1 event of seizure. There were no apparent differences between treatment groups in laboratory assessments over time.

No differences were apparent between treatment groups when examining most vital signs, PEs, and ECG. However, there was a decline in weight in the bryostatin groups, which was more prominent in the higher dose group: 20µg bryostatin treatment group (mean loss of -1.65 ± 2.77 kg) and the 40µg bryostatin treatment group (-2.98 ± 2.10 kg), while there was a slight weight gain in the placebo treatment group (0.442 ± 2.52 kg). Further, 5 subjects in the 40µg bryostatin treatment group had 5 TEAEs of weight decreased, 3 of which were judged to be related to the IP. No weight related TEAEs were observed in the 20µg bryostatin dose group.

There were no differences between treatment groups on the C-SSRS as most subjects did not have suicidal thoughts during the trial, and there were no attempts at suicide by any subject during the trial.

Details regarding adverse events can be found on ClinicalTrials.gov, study identifier: NCT02431468.

2.1.2.4 *Efficacy*

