4.3 Study Endpoints

4.3.1 Safety Assessments

- Treatment emergent AEs and SAEs
- Vital signs, hematology, blood chemistry, and physical examination including body weight
- ECG parameters
- C-SSRS

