9.7 Safety Assessments

Unblinded summaries and listings of safety data will be provided to the Data Safety Monitoring Board, as described in Section 8. Analyses will be performed by an independent unblinded statistician so that study investigators and other sponsor personnel (and contractors) involved in study monitoring, data processing and other aspects of the study remain blinded.

CONFIDENTIAL

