6 PLANNED ANALYSES

All statistical analyses described in this Statistical Analysis Plan (SAP) were finalized and approved by the trial Principal Investigator (PI), [name], Chief Scientific Officer, [name], Lead Statistician, [name], and WCT Statistician, prior to the complete unmasking of the data. In addition, the methods described herein are given precedence over the analytical plans outlined in the clinical protocol. However, no SAP prepared in advance of the data can be final until the data are unmasked. The final Clinical Study Report (CSR) may contain additional tables or statistical tests if warranted by the data obtained. The justification for any such additional analyses will be fully documented in the final CSR.

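### The DSMB package listed in SAP 8 holds only background and adverse-event outputs, with no post-baseline weight, laboratory, vital-sign, ECG or C-SSRS data, and AE tables can miss a mean shift below AE level

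*SAP*

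**What the plan says.** SAP 8 sets two safety reviews, "when 30 subjects have received four doses of study drug, followed by additional safety analyses when 60 subjects have received a similar number of doses". It continues "Following tables and listings will be prepared for DSMB review" and names the outputs.

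- **Tables (nine):** demographics, disease history and medical history; TEAEs, serious TEAEs and AEs of special interest, each with a version by relationship to treatment.
- **Listings (eight):** the same three background items; pre-treatment AEs, TEAEs, serious TEAEs, TEAEs leading to treatment discontinuation and fatal TEAEs.

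Protocol 4.3.1 declares a wider set of safety assessments. Besides AEs, ECG and the C-SSRS it names "Vital signs, hematology, blood chemistry, and physical examination including body weight". Protocol 6.0.1 says that safety will be judged by AEs and by change from baseline in these measures. Protocol 9.7 says "Unblinded summaries and listings of safety data will be provided to the Data Safety Monitoring Board", with no restriction to AEs, and Protocol 8 also speaks of safety data tables and listings.

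SAP 6 says that "the methods described herein are given precedence over the analytical plans outlined in the clinical protocol", so the narrower SAP list is the operative one. SAP 9, which records changes from the protocol, does not mention the narrowing.

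On the earlier trial NTRP101-202, Protocol 2.1.2.3 reports that "there was a decline in weight in the bryostatin groups, which was more prominent in the higher dose group". It gives a "mean loss of -1.65 ± 2.77 kg" at 20 µg and a mean gain of 0.442 kg (SD 2.52) on placebo. It then adds "No weight related TEAEs were observed in the" 20 µg group.

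**The concern.** The board's task is to protect subjects while the trial runs. Under SAP 8 it sees a laboratory value, blood pressure, ECG finding, C-SSRS response or weight only if an investigator has recorded it as an AE. That route works subject by subject. It does not show a shift in a group mean when each individual change looks unremarkable. NTRP101-202 had such a shift in weight at the dose now under study, and no AE at that dose recorded it. If the same happened here, the listed package would show the board nothing about it at either review, although the data would be in the trial database.

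**Working it through.** The plan states no figure to reproduce. The check has three parts: what is listed, what the earlier trial shows, and what the board could see if the outputs were added.

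**1. Declared assessments against the SAP 8 list**

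| Assessment (Protocol 4.3.1) | In SAP 8? | Planned final table (SAP 11) |
|---|---|---|
| AEs, SAEs | yes | 14.3.1.x |
| Laboratory | no | 14.3.4.1 to 14.3.4.4 |
| Vital signs | no | 14.3.6.1 |
| Weight change | no | 14.3.6.2 |
| ECG | no | 14.3.7.1, 14.3.7.2 |
| C-SSRS | no | 14.3.7.3, 14.3.7.4 |

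Protocol 9.1 counts body weight as a demographic item, so a baseline weight may be shown. What is missing is post-baseline weight.

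**2. Weight in NTRP101-202 (Protocol 2.1.2.3)**

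Arm sizes follow from the treatment-related TEAE percentages: 17 subjects are 37.0%, so n = 46 at 20 µg; 8 are 16.7%, so n = 48 on placebo; 24 are 51.1%, so n = 47 at 40 µg. The sum, 46 + 48 + 47 = 141, matches the treated total in Protocol 2.1.2.2.

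- Difference, 20 µg minus placebo: -1.65 - 0.442 = -2.09 kg.
- SE = sqrt(2.77²/46 + 2.52²/48) = 0.547.
- z = -2.092/0.547 = -3.83; approximate 95% CI -2.092 ± 1.96 × 0.547, or -3.16 to -1.02 kg.
- If only 35 per arm had a weight, SE = sqrt((2.77² + 2.52²)/35) = 0.633 and |z| = 3.3.
- Weight-related TEAEs at 20 µg: 0 of 46, one-sided 95% upper bound 1 - 0.05^(1/46) = 6.3%.

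A clear difference in measured weight went with no weight AE at that dose.

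**3. What an added weight table could show**

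Assume that the NTRP101-202 difference is fully present at the review, with common SD sqrt((2.77² + 2.52²)/2) = 2.65. Expected z = 2.092/(2.65 × sqrt(2/n)). The chance of nominal two-sided p < 0.05 is Φ(z - 1.96).

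| Per arm with a weight | Expected z | Chance |
|---|---|---|
| 10 | 1.77 | 42% |
| 15 | 2.16 | 58% |
| 24 | 2.74 | 78% |
| 30 | 3.06 | 86% |

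The rows for 15 and 30 are best cases for the 30- and 60-subject reviews at 1:1 allocation. Dose 4 falls at Week 5 (Protocol 6.1.6). Weight is taken at physical examinations, and the first on study is at Week 7 (Protocol 6.0.1.2 and 6.1.7; SAP 6.12.5). Subjects who have just reached the trigger have no on-study weight, while earlier enrollees do. By contrast, laboratory, ECG and C-SSRS data start at Week 2, and vital signs are taken at every visit.

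**4. Grouping**

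Protocol 8 describes displays by masked Group A and Group B. It also says that the reviews are summarized for all subjects together and not split by treatment. Protocol 9.7 calls the summaries unblinded. Pooling matters: in a 1:1 pool the NTRP101-202 changes would average (-1.65 + 0.442)/2 = -0.60 kg, with no comparison group.

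**The case against.** The strongest defence has three parts.

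**The documents route abnormalities into AEs.** Clinically significant physical and laboratory findings become AEs, and the investigator makes an AE determination after any positive C-SSRS response. In NTRP101-202 this route did pick up weight at 40 µg: five weight-decreased TEAEs, three judged related. This stands. A reader might infer that AE reporting fails for weight altogether, and the documents do not support that. They support a narrower statement: it can miss a mean shift below AE level, as at 20 µg.

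**The list is not called exhaustive.** No DSMB charter is among the documents, Protocol 9.7 promises safety data generally, and Protocol 8 has the supporting biostatistician approve the content of listings. The board may therefore receive more. This also stands, but the SAP then needs to say so, because its named list takes precedence as written.

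**The evidence covers weight only.** NTRP101-202 reported no apparent differences in laboratory results, ECG, most vital signs or C-SSRS. It would be wrong to infer that the earlier trial gave signals in those areas. Adding those outputs rests on the protocol's own declaration of safety assessments, not on a prior signal.

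Two further inferences are tempting. One is that 14 planned doses against 7 in NTRP101-202 makes the gap worse at these reviews. The trigger is four doses, so much of the second-course exposure falls outside both reviews whichever tables are shown. The other is that a weight effect would certainly be seen at 60 subjects. That assumes a weight for every subject and the full effect already present, and the documents do not say when the NTRP101-202 change was measured.

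**Conclusion.** The concern holds in limited form. As listed, the SAP 8 package is narrower than the protocol's declared safety assessments and its promise to the board, and it could leave a mean shift below AE level unseen. Weight is the one supported example: -2.09 kg against placebo at the dose under study, z about 3.8 (about 3.3 if only 35 per arm were weighed), with no weight-related TEAE at that dose. The figures assume that the arm sizes recovered from percentages are the weight denominators. The expected z of about 3.1 at 30 per arm is a best case. The documents do not establish that the board will in practice see nothing else, since a charter could add outputs. This should be corrected, because the data are collected and the tables are already defined.

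**What to change.** Add to SAP 8, by masked group, these outputs from SAP 11: 14.3.6.1 and 14.3.6.2 (vital signs, weight), 14.3.4.1 to 14.3.4.4 (laboratory), 14.3.7.1 to 14.3.7.4 (ECG, C-SSRS) and 14.3.5.1 (exposure). If a charter already supplies them, cite it in SAP 8 instead.

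Reconcile the statements on grouping in Protocol 8 with each other and with Protocol 9.7, so that it is clear the board's displays are split by group. If the sentence about not separating by treatment refers only to the written summary of each review, say so.

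The cost is small programming time to run planned tables at two extra data cuts. Weight will be incomplete at each review because of the Week 7 and Week 5 timing, so the weight table should show the number of subjects with a post-baseline value in each group.
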